1.3.2 Schedule of Activities for the Treatment Period

Study Period	Treatment Period Cycle = 21 days								Notes
	Cycle 1				Cycle 2-7			Cycles \geq 8	
Visit Timing									
Visit Day (Days)	1	3	5	8	1	8 (Cycles 2-3 only)	15 (Cycles 2-3 only)	1	
Visit Window	+1	\pm 1	\pm 1	\pm 1	+3	\pm 3	\pm 3	\pm 3	The visit window is +3 days for C2D1 and \pm 3 days for Day 1 of subsequent cycles.
Pembrolizumab Administration Cohorts 1, 2, 3, and 4					X			X	For the first 3 doses of V938 (C1D1, C1D3, and C1D5), time of administration between 2 doses must be at least 24 hours apart.
Pembrolizumab Administration Cohorts 2a, 3a, or 4a; and the Expansion Cohorts	X				X			X	
V938 Administration	X	X	X	X	X				On visits when both V938 and pembrolizumab are administered, V938 IT injection will be administered prior to pembrolizumab IV infusion. See Pharmacy Manual for more details.
24-hour Observation Period	X	X							For Dose-escalation Cohorts , a 24-hour inpatient observation period following V938 administration on C1D1 and C1D3 is required for each participant. Observation for the remaining V938 doses will be at the discretion of the investigator, per local Institutional Review Board, Ethics Review Committee, and/or Health Authority mandate. For Expansion Cohorts , the requirement for 24-hour inpatient observation for the first 2 doses may be optional based on the updated safety profile.

Study Period	Treatment Period Cycle = 21 days								Notes
	Cycle 1				Cycle 2-7			Cycles \geq 8	
Visit Timing									
Visit Day (Days)	1	3	5	8	1	8 (Cycles 2-3 only)	15 (Cycles 2-3 only)	1	For all cycles: Up to 35 cycles of pembrolizumab and up to 7 cycles (ie, 10 doses) of V938. All cycles are 21 days. For Cycle 2 and 3, D8 and D15 visits including safety assessments can be omitted if V938 is not dosed for that cycle due to interruption or discontinuation.
Visit Window	+1	± 1	± 1	± 1	+3	± 3	± 3	± 3	The visit window is +3 days for C2D1 and ± 3 days for Day 1 of subsequent cycles.
Clinical Procedures/Assessments									

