Tumor Imaging, RECIST 1.1, iRECIST, and/or itRECIST Response Assessment									Tumor imaging (CT or MRI) for solid tumors and medical photography of cutaneous lesions should be performed every 9 weeks (± 7 days) after the first dose for the first 54 weeks then every 12 weeks thereafter, following calendar days , and should not be adjusted for delays in cycle starts. Continue imaging schedule until disease progression, discontinuation, or the start of anticancer treatment. Please refer to Imaging Manual for detailed information on medical photography.
Medical Photography (Cutaneous Lesions)									Obtain for all injected lesions for every IT injection performed. If imaging is used to guide injection (eg, CT, ultrasound, fluoroscopy), capture images to document injected lesions. If injection by visualization or palpation, it is recommended to capture photographs with skin markers to show injected lesions.
Lesion Injection Scan									
Physical Examination		X	X	X	X	X	X	X	Directed physical examinations to be performed unless a full examination is deemed necessary. To be performed on Days 3, 5, and 8 of Cycle 1; on Days 1, 8, and 15 of Cycle 2, and on Day 1 of every cycle thereafter.
Weight	X				X			X	Every other cycle (ie, Cycles 1, 3, 5, 7, 9, etc.).

Study Period	Treatment Period Cycle = 21 days								Notes
	Cycle 1				Cycle 2-7			Cycles \geq 8	
Visit Timing	1	3	5	8	1	8 (Cycles 2-3 only)	15 (Cycles 2-3 only)	1	
Visit Day (Days)	1	3	5	8	1	8 (Cycles 2-3 only)	15 (Cycles 2-3 only)	1	
Visit Window	+1	± 1	± 1	± 1	+3	± 3	± 3	± 3	The visit window is +3 days for C2D1 and ± 3 days for Day 1 of subsequent cycles.
Vital Signs * (temperature, pulse, respiratory rate, and blood pressure)	X	X	X	X	X	X	X	X	For Cycle 1, to be measured within 1 h prior to dosing, and 2, 4, and 6 hours (\pm 30 min for each timepoint) after V938 administration in Cycle 1. For Cycle 2 to Cycle 7, to be measured within 1 h prior to dosing, and 2 and 4 hours (\pm 30 min for each timepoint) after V938 administration. In addition, for Cycles 2 and 3, to be measured on Day 8 and Day 15. For Cycle 8 and beyond, to be measured within 1 h prior to each dosing with pembrolizumab. * For participants who interrupt or discontinue V938 but continue pembrolizumab, to be measured within 1 h prior to dosing with pembrolizumab.
ECOG Performance Status					X			X	ECOG PS may be performed up to 72 hours prior to dosing.
Concomitant Medication	X	X	X	X	X	X	X	X	

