4.1.1 Dose-escalation Phase

The primary goal for the dose-escalation phase is to evaluate safety, tolerability, and PK/pharmacodynamics of V938 as monotherapy and in combination with pembrolizumab, with an ultimate goal of determining a RP2D of V938 in combination with pembrolizumab.

V938 IT will be evaluated at 4 dose levels: 1×10^7 PFU (Dose Level 1, evaluated via Cohort 1), 1×10^8 PFU (Dose Level 2, evaluated via Cohort 2 and possibly Cohort 2a), 3×10^8 PFU (Dose Level 3, evaluated via Cohort 3 and Cohort 3a) and 5×10^8 PFU (Dose Level 4, evaluated via Cohort 4 and Cohort 4a). The dosing schedule of V938 is the same across all

the cohorts with 4 doses during Cycle 1 on Days 1, Day 3, Day 5, Day 8 and 1 dose each on Day 1 of Cycle 2 to Cycle 7. Therefore, V938 will be dosed for a maximum of 10 doses.

Pembrolizumab will be dosed 200 mg IV Q3W for a maximum of 35 doses (in approximately 24 months) across all cohorts. Pembrolizumab dosing will start on C2D1 for Cohorts 1-4, which allows to evaluate safety and PK/pharmacodynamics of V938 as monotherapy for the first cycle. Pembrolizumab dosing for Cohorts 2a-4a will start on C1D1.

In general, dose escalation will progress using an mTPI design [Ji Y, Li Y, Bekele BN 2007] with the goal to identify the MTD and/or maximum administered dose of V938 administered as combination with pembrolizumab ([Figure 1](#)). Intermediate doses of V938 may also be explored with additional cohorts, depending on the combined safety, PK, and pharmacodynamics data available at each dose level.

During dose escalation, 3 to 6 participants will be initially enrolled to each dose level starting with Cohort 1. Treatment assignments will be nonrandom via an interactive voice response system/integrated web response system (IVRS/IWRS). Enrollment at the next dose level will begin once all participants in the current dose level complete DLT evaluation and a dose-escalation decision has been made. The DLT evaluation period for Cohorts 1-4 is 42 days (Cycle 1 + Cycle 2) to evaluate safety and PK/pharmacodynamics of 1 cycle of V938 as monotherapy and 1 cycle of V938 in combination with pembrolizumab; the DLT evaluation period for Cohorts 2a-4a is 21 days (Cycle 1 only) as pembrolizumab and V938 both start on C1D1.

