5.5 Participant Replacement Strategy in Dose Escalation

In order to adequately evaluate the safety of the doses administered in this study, all participants enrolled must meet the criteria for evaluability for Cycle 1 and Cycle 2 for Cohorts 1-4 of dose escalation and must meet the criteria for evaluability for Cycle 1 for Cohorts 2a-4a. Participants are considered nonevaluable and will be replaced if:

They are allocated but not treated.

They discontinue from the study prior to completing all the safety evaluations for reasons other than treatment-related AEs.

They receive less than 75% of the total V938 PFU injection or pembrolizumab infusion in the DLT evaluation period (eg, if the infusion had to be discontinued due to an infusion reaction) and did not experience a DLT.

Participants who are not evaluable will be replaced unless accrual to the cohort has stopped. Nonevaluable participants will not be counted toward the total number of participants in the cohort for DLT evaluation.

If a participant experiences a DLT in the DLT evaluation period, study intervention may be discontinued following discussion between the Sponsor and investigator. However, if the participant is deriving clinical benefit from the study intervention, the participant may be allowed to continue after discussion between the Sponsor and the investigator.

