Participants should receive appropriate supportive care measures as deemed necessary by the treating investigator. Suggested supportive care measures for the management of AEs with potential immunologic etiology are outlined along with the dose modification guidelines in [Table 8](#). Where appropriate, these guidelines include the use of oral or IV treatment with corticosteroids, as well as additional anti-inflammatory agents if symptoms do not improve with administration of corticosteroids. Note that several courses of steroid tapering may be necessary as symptoms may worsen when the steroid dose is decreased. For each disorder, attempts should be made to rule out other causes such as metastatic disease or bacterial or viral infection, which might require additional supportive care. The treatment guidelines are intended to be applied when the investigator determines the events to be related to pembrolizumab.

Note: If after the evaluation of the event, it is determined not to be related to pembrolizumab, the investigator does not need to follow the treatment guidance. Refer to [Table 8](#) for guidelines regarding dose modification and supportive care.

It may be necessary to perform conditional procedures such as bronchoscopy, endoscopy, or skin photography as part of evaluation of the event.

6.6 **Dose Modification (Escalation/Titration/Other)**

6.6.1 **Dose Administration/Escalation**

Details on preparation and administration of V938 and pembrolizumab are provided in the appropriate Pharmacy/Laboratory Procedures Manual.

6.6.2 **Definition of Dose-limiting Toxicity**

All toxicities will be graded using CTCAE Version 4.0, with exception of CRS, based on the investigator assessment. The CRS grading system used in this protocol is adapted from the ASTCT Consensus Grading for CRS [Lee, D. W., et al 2019].

The DLT observation period for Cohorts 1-4 will be 42 days during Cycles 1 and 2 (ie, the first monotherapy run-in cycle [Cycle 1] and the first combination therapy cycle [Cycle 2]). The DLT observation period for Cohorts 2a-4a will be 21 days during Cycle 1 only.

The occurrence of any of the following toxicities during the DLT observation period will be considered a DLT, if assessed by the investigator to be possibly, probably, or definitely related to study intervention administration:

1. Grade 4 nonhematologic toxicity (not laboratory)
2. Grade 4 hematologic toxicity lasting ≥ 7 days, except thrombocytopenia:

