 - a. Grade 4 thrombocytopenia of any duration
 - b. Grade 3 thrombocytopenia associated with clinically significant bleeding
3. Grade 3 nonhematologic AE with the following exceptions:
 - a. Grade 3 fatigue lasting ≤ 72 hours
 - b. Grade 3 diarrhea, nausea, or vomiting lasting ≤ 72 hours without use of antiemetics or antidiarrheals per standard of care
 - c. Grade 3 rash without use of corticosteroids or anti-inflammatory agents per standard of care.
4. Any Grade 3 or Grade 4 nonhematologic laboratory value if:
 - a. Clinically significant medical intervention is required to treat the participant, or
 - b. The abnormality leads to hospitalization, or
 - c. The abnormality persists for >1 week
 - d. The abnormality results in a DILI (see Sections 8.4.1 and 8.4.7 for criteria)

Exceptions: Clinically nonsignificant, treatable, or reversible laboratory abnormalities including liver function tests, uric acid, etc.
5. Febrile neutropenia Grade 3 or Grade 4:
 - a. Grade 3 is defined as ANC $<1000/\text{mm}^3$ with a single temperature of $>38.3^\circ\text{C}$ (101°F) or a sustained temperature of $\geq 38^\circ\text{C}$ (100.4°F) for more than 1 hour.
 - b. Grade 4 is defined as ANC $<1000/\text{mm}^3$ with a single temperature of $>38.3^\circ\text{C}$ (101°F) or a sustained temperature of $\geq 38^\circ\text{C}$ (100.4°F) for more than 1 hour, with life-threatening consequences and urgent intervention indicated.
6. Prolonged delay (>2 weeks) in initiating Cycle 3 (for Cohorts 1-4) or Cycle 2 (for Cohorts 2a-4a) due to study intervention-related toxicity.

7. Any study intervention-related toxicity that causes the participant to discontinue intervention during the DLT evaluation period.
8. Missing >1 injection of V938 as a result of drug-related AE(s) during the first 2 cycles (for Cohorts 1-4) or during the first cycle (for Cohort 2a-4a).
9. Grade 5 toxicity.

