6.6.4 Guidelines for Dose Modification due to Adverse Events

Adverse events (both nonserious and serious) associated with V938 and pembrolizumab exposure may represent an immunologic etiology. These AEs may occur shortly after the first dose or several months after the last dose of treatment.

The CTCAE 4.0 must be used to grade the severity of AEs with exception of CRS. CRS is graded using the grading system adapted from the ASTCT Consensus Grading for CRS. The investigator may attribute each toxicity event to V938 alone, to pembrolizumab alone, or to the combination, and modify the dose according to [Table 5](#) and/or [Table 8](#).

Reduction or holding of 1 agent and not the other agent is appropriate if, in the opinion of the investigator, the toxicity is clearly related to 1 of the study interventions. For example, in combination, if V938 is held due to an AE attributed to that drug, then pembrolizumab may continue to be administered, and vice versa. Appropriate documentation is required regarding to which drug the investigator is attributing the AE. If, in the opinion of the investigator, the toxicity is related to the combination of 2 agents, then both drugs should be held according to recommended dose modifications.

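### The waiver of Cycle 2 Day 8 and Day 15 visits when V938 is not dosed has no exception for Cohorts 1-4, whose DLT window includes Cycle 2

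*Combined protocol and SAP*

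**What the plan says.** The notes column of the treatment-period schedule (1.3.2) allows the following: "For Cycle 2 and 3, D8 and D15 visits including safety assessments can be omitted if V938 is not dosed for that cycle". The stated reasons are interruption or discontinuation of V938. No cohort is named.

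Other parts of the protocol bear on who can use the waiver and when:

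- Section 4.1.1: "Pembrolizumab dosing will start on C2D1 for Cohorts 1-4". Cycle 1 is V938 alone and Cycle 2 is the first combination cycle.
- Section 6.6.2: "The DLT observation period for Cohorts 1-4 will be 42 days during Cycles 1 and 2". For Cohorts 2a-4a the window is Cycle 1 only.
- Section 6.6.4: "if V938 is held due to an AE attributed to that drug, then pembrolizumab may continue to be administered".
- Section 5.5 makes a DLT-free participant nonevaluable if "They receive less than 75% of the total V938 PFU injection or pembrolizumab infusion in the DLT evaluation period". It also requires Cohorts 1-4 to be evaluable for both Cycle 1 and Cycle 2.
- Section 6.6.2 counts as a DLT "Missing >1 injection of V938 as a result of drug-related AE(s) during the first 2 cycles (for Cohorts 1-4", so a single missed injection does not qualify. It also lists "Grade 4 thrombocytopenia of any duration".

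Without the waiver, 1.3.2 schedules blood count, chemistry and vital signs on Days 8 and 15 of Cycle 2, and directed examinations "on Days 1, 8, and 15 of Cycle 2, and on Day 1 of every cycle thereafter". No other section restores these visits for a participant still inside the DLT window. Section 7.1 asks for all visits in the schedule, and the schedule already contains the waiver.

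**The concern.** The waiver makes sense where the extra visits exist only to watch a V938 dose that was not given. In Cohorts 1-4 the Cycle 2 visits do more. They cover the three weeks after the first pembrolizumab dose, and those weeks count toward the DLT assessment. A participant can therefore have V938 held, receive pembrolizumab for the first time, skip both visits and still enter Table 1 as DLT-free.

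The path is realistic. Table 5 requires V938 to be held for a Grade 3 hematologic toxicity lasting more than 5 days, and most such events are not DLTs under 6.6.2. Section 8.1.11.1 also permits interruptions for logistical reasons. In that case no abnormal value exists to prompt extra testing.

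At stake is a clinically silent laboratory DLT that goes unseen. Initial cohorts have 3 to 6 participants, so one such event can change a dose decision. Under 4.3.4, an escalate decision for Cohort 3 opens both Cohort 4 and Cohort 3a, while a stay decision opens only Cohort 3a.

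**Working it through.** **The plan's own figure.** Cycles are 21 days, so 2 × 21 = 42 days, as stated for Cohorts 1-4.

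**Who stays evaluable.** V938 doses planned in the window are C1D1, C1D3, C1D5, C1D8 and C2D1, or 4 + 1 = 5. Assume that the 75% rule applies to the window total and that each given dose is complete. Share received = (5 − missed)/5.

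- One missed: 4/5 = 80%. This is at least 75%, so the participant is evaluable. One is not more than one, so it is not a DLT.
- Two missed: 3/5 = 60%. This is a DLT if drug-related; otherwise the participant is nonevaluable and replaced, unless another DLT occurred.

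The gap therefore concerns participants who miss C2D1 alone.

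**Time to the first scheduled draw (nominal days).** C1D8 = 8, C2D1 = 22, C2D8 = 29, C2D15 = 36, C3D1 = 43. Pre-cycle tests fall within 72 hours before a cycle: days 19-22 for Cycle 2 and days 40-43 for Cycle 3.

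- Visits kept: 29 − 22 = 7 days after the first pembrolizumab dose.
- Visits waived: 40 − 22 = 18 to 43 − 22 = 21 days.
- Longest scheduled laboratory gap after C1D8 in Cycle 1, any cohort: 19 − 8 = 11 to 22 − 8 = 14 days.

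**Does a scheduled draw fall within an episode?** For an episode of L days starting on day t, a draw on day d hits it if t ≤ d ≤ t + L − 1. Count the hits over the 20 onset days after Day 1 of the cycle. For Cycle 2, onsets are days 23-42, with draws on {29, 36, x} kept or {x} waived, x = 40-43. For Cycle 1, onsets are days 2-21, with draws on {8, y}, y = 19-22. Episode length is an assumption, so a range is shown.

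| Episode length | Cycle 2 waived | Cycle 2 kept | Cycle 1 as scheduled |
|---|---|---|---|
| 3 days | 2-3 of 20 | 8-9 | 5-6 |
| 5 days | 4-5 | 14-15 | 9-10 |
| 7 days | 6-7 | 18-20 | 13-14 |
| 10 days | 9-10 | 18-20 | 16-17 |

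Moving Days 8 and 15 anywhere in their ±3-day windows gives kept counts of 6-9, 10-15, 12-20 and 15-20. All remain above the waived counts.

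**Which rows matter.** Among hematologic DLTs, the 3- and 5-day rows bear only on transient Grade 4 thrombocytopenia, since other Grade 4 hematologic toxicity must last at least 7 days. The longer rows bear on that criterion and on nonhematologic laboratory abnormalities lasting more than 1 week. A hit does not document duration. It triggers the repeat testing in 8.3.4 and the follow-up in 8.3.4.1, and without a draw neither starts.

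**Effect on Table 1.** Inputs are the Beta(1,1) prior, target 0.30 and ε = 0.03. With x DLTs in n participants and F the Beta(1 + x, 1 + n − x) distribution function, compare E = F(0.27)/0.27, S = [F(0.33) − F(0.27)]/0.06 and D = [1 − F(0.33)]/0.67. The largest decides.

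| DLTs/n | E | S | D | Decision |
|---|---|---|---|---|
| 0/3 | 2.652 | 1.375 | 0.301 | E |
| 1/3 | 1.096 | 1.760 | 0.893 | S |
| 1/6 | 2.235 | 2.115 | 0.402 | E |
| 2/6 | 1.060 | 2.259 | 0.863 | S |

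These match Table 1. One unseen DLT turns 1/3 into 0/3, or 2/6 into 1/6, and stay becomes escalate.

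**The case against.** The strongest objection concerns evaluability. Section 5.5 never says that the 75% is cumulative. It asks Cohorts 1-4 to be evaluable for Cycle 1 and Cycle 2, and section 4.1.1 says the 42-day window is there to observe a cycle of combination dosing. Read per cycle, a participant with no Cycle 2 V938 received 0% of that cycle's dose. If DLT-free, that participant is replaced, and the Table 1 effect vanishes. This stands as an alternative reading. Section 5.5 refers to the total V938 given in the evaluation period, which favors the cumulative reading but does not settle it. The missing exception in 1.3.2 remains either way.

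A reader might take the hit counts as the share of DLTs that would be missed. The documents do not support that. Section 6.6.2 excepts many reversible or treatable nonhematologic laboratory abnormalities, liver tests among them. The V938 risks anticipated in 2.3, and the cytokine release syndrome reported in 6.6.4.1.1, are mostly symptomatic and would surface through AE reporting, which stays continuous. No event rate is given. Where V938 was held for a known AE, follow-up of that event continues under 8.4.3 and 8.3.4.1.

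Lighter monitoring without V938 is also a coherent choice. From Cycle 4 the schedule has only pre-cycle laboratory tests even while both drugs continue. Those cycles, however, lie outside every DLT window. Inside the windows, the waived cycle falls below the schedule's own Cycle 1 standard.

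Finally, Amendment 8 closes the study. The amendment history supplied does not show when the waiver was introduced, so it may not have applied while Cohorts 1-4 were in their windows. That limits the practical value of editing the schedule and makes a CSR count the more useful remedy.

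**Conclusion.** The point holds in a narrow form. The waiver can remove both scheduled mid-cycle safety visits from the second half of the Cohort 1-4 DLT window, and nothing elsewhere puts them back. The first scheduled laboratory test after the first pembrolizumab dose then moves from 7 days to 18-21 days.

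The effect on DLT counting rests on three conditions: the cumulative reading of 5.5, a participant who misses only C2D1 V938 while receiving pembrolizumab, and a site that chooses to use the waiver. The toxicity at issue is mainly silent Grade 4 thrombocytopenia, then silent Grade 4 hematologic toxicity of at least 7 days or laboratory abnormalities beyond 1 week. The number of participants cannot be estimated from the documents and is probably small.

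A reader might infer that the RP2D is compromised. The documents do not support that. It is chosen from Cohorts 2a-4a, which have their own DLT evaluation in Cycle 1, on the totality of the data. Any influence from Cohorts 3 and 4 is indirect, through which cohorts open. Nor does the waiver end safety monitoring: AE reporting, follow-up of known events and the pre-Cycle 3 tests all remain.

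This is a cheap improvement of low priority.

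**What to change.** In 1.3.2, add one sentence: the Day 8 and Day 15 waiver does not apply within a cohort's DLT observation period, that is, in Cycle 2 of Cohorts 1-4. It can stand for Cycle 3 in all cohorts and for Cycle 2 of Cohorts 2a-4a and the expansion arms.

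If Cohorts 1-4 are already complete, report in the CSR how many of their DLT-evaluable participants had C2D8 or C2D15 omitted under the waiver. A count of zero closes the point.

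The cost is one sentence or one count. The burden is at most two visits, already planned in the schedule, for a few participants.

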1.3.3 Schedule of Activities for the End-of-Treatment and Posttreatment Follow-up Periods

Study Period	End of Treatment (EOT)/ Discontinuation	Posttreatment Period			Notes
		30-Day Safety Follow-up Visit	Imaging Follow-up	Survival Follow-up	
Visit Timing		30 days after the last dose	Approximately every 9 weeks	Approximately every 12 weeks	
Visit Window (Days)	±7	+7	±7	±14	
Administrative Procedures					
Concomitant Medication	X	X			
Efficacy Procedures					See Imaging Manual – All imaging visits have a ± 7-day window
Tumor Imaging, RECIST 1.1 and iRECIST Response Assessment	X		X		
Medical Photography (Cutaneous Lesions)	X		X		
New Anticancer Therapy Status	X	X	X		
Survival Status Monitoring		← →			Upon Sponsor request, participants may be contacted for survival status at any time during the course of the study. After confirmed disease progression, each participant will be contacted by telephone for survival until participant withdrawal of consent, becoming lost to follow-up, death, or the end of the study.
Safety Assessments and Procedures					See Laboratory Procedures Manual for collection and management of samples.
Adverse Event Monitoring	X	X			
Full Physical Examination	X	X			
Weight	X	X			
Vital Signs	X	X			Temperature, pulse, respiratory rate, and blood pressure
ECOG Performance Status	X	X			
CBC with Differential	X	X			
Chemistry Panel	X	X			

Study Period	End of Treatment (EOT)/ Discontinuation	Posttreatment Period			Notes
		30-Day Safety Follow-up Visit	Imaging Follow-up	Survival Follow-up	
Visit Timing		30 days after the last dose	Approximately every 9 weeks	Approximately every 12 weeks	
Visit Window (Days)	±7	+7	±7	±14	
Pregnancy Test for WOCBP – Urine or Serum hCG		X			For WOCBP, perform every 30 days during a 120-day period following last dose, and as required locally. If a urine pregnancy test cannot be confirmed as negative, a serum pregnancy test is required.
Thyroid Function (TSH, T3, FT3, T4, FT4)		X			

Abbreviations: CBC = complete blood count; CT = computed tomography; ECOG = Eastern Cooperative Oncology Group; EOT = end of treatment; FT3 = free triiodothyronine; FT4 = free thyroxine; hCG = human chorionic gonadotropin; MRI = magnetic resonance imaging; NDV = Newcastle Disease Virus; PET = positron emission tomography; PK = pharmacokinetic(s); RNA = ribonucleic acid; RECIST v1.1 = Response Evaluation Criteria In Solid Tumors, version 1.1; iRECIST = immune-related RECIST; RNA = ribonucleic acid; T3 = triiodothyronine; T4 = thyroxine; TSH = thyroid-stimulating hormone; WOCBP = women of childbearing potential.

